Based on our preliminary work, our research group obtained funding from the Laerdal Foundation to conduct an internal pilot trial of the DOSE VF protocol (<https://clinicaltrials.gov/ct2/show/NCT03249948>) previously approved by the Sunnybrook Health Sciences Center REB. The pilot trial was designed to determine the feasibility of conducting a full-scale randomized trial in this population.^{17,18} The pilot RCT completed on September 9, 2019, trained over 2,500 paramedics in the technique of DSED and vector change defibrillation (VC). The pilot took place in four paramedic services in Ontario (Toronto, Peel, Halton and Simcoe) with all services actively enrolling patients. All paramedics received in-person training using a combination of didactic, video and simulated scenarios prior to the study launch. All eligible patients with refractory VF (n=152) in the participating paramedic services have had paramedics successfully apply both VC and DSED. The DOSE-VF Pilot RCT demonstrated that the protocol is feasible with 89.5% of patients receiving the treatment they were randomized to and 90.2% of patients receiving an intervention shock prior to shock 6 in the resuscitation. As well, no safety concerns were noted (no reports of defibrillator damage, skin burns, inadvertent shocking of paramedics or bystanders) and was well accepted by paramedics in the field. We have as well been able to determine the number of cases occurring in each service during the pilot RCT (varying from 1.4-6.1 cases/month) allowing us to accurately calculate the number of patients required to perform an adequately powered definitive RCT. Finally, we observed that the rate of VF termination and ROSC were greater in both

interventions then standard defibrillation. Specifically, in the standard group, 66.6% of cases resulted in VF termination, compared to 82.0% in VC and 76.3% in the DSED group. ROSC was achieved in 25.0%, 39.3% and 40.0% of standard, VC and DSED groups, respectively. The DOSE-VF pilot RCT has established the feasibility of proceeding with a definitive, adequately powered RCT to determine whether employing a standardized approach to alternative defibrillation strategies early in the treatment of refractory VF may impact clinical outcomes.

Objective: The objective of this study is to compare two novel therapeutic defibrillation strategies (DSED and VC) against standard practice for patients remaining in refractory VF during out-of-hospital cardiac arrest.

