All paramedics treating patients during out-of-hospital cardiac arrest follow a provincial protocol for treatment of patients in VF (**Appendix 1**). Cardiopulmonary resuscitation (CPR) will be performed prior to defibrillator pad application. Each rhythm analysis will occur at standard two-minute intervals. VF will be determined by paramedic manual defibrillator analysis or semi-automatic defibrillator analysis by participating fire services, after which a shock will be provided. For all patients, the first three shocks will occur with defibrillation pads placed in the anterior-lateral position. Epinephrine and antiarrhythmic medication (amiodarone or lidocaine) will be provided as per provincial protocol. For eligible patients remaining in VF after three consecutive shocks (following two-minute CPR intervals) that are delivered by paramedics or participating fire services (defibrillation shocks provided by bystanders prior to EMS arrival will not be counted), all subsequent defibrillations will be randomized to one of the following treatment strategies:

Strategy 1 (**Standard Defibrillation**): For paramedic services randomized to standard defibrillation, all subsequent defibrillation attempts will occur through pads placed in an anterior-lateral configuration as noted in **Appendix 1**.

Strategy 2 (**VC Defibrillation**): For paramedic services randomized to VC defibrillation, all subsequent shocks will be delivered using anterior-posterior pad placement, as noted in Appendix 1. Transfer of pads to the anterior-posterior position from the initial standard anterior-lateral configuration will occur during the two-minute cycle of CPR following the third shock with minimal interruptions in CPR.

Strategy 3 (**DSED**): For paramedic services randomized to DSED, paramedics will apply a second set of defibrillation pads as soon as possible after the first three shocks (via a second

paramedic or fire defibrillator) in the anterior-posterior position, as noted in **Appendix 1**.

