All tests will be 2-sided with $p < 0.05$ denoting statistical significance. The unit of analysis for the comparisons will be the individual patient. All patients will be analyzed according to randomized treatment assignment (intention-to-treat analysis). Based on the DOSE VF pilot RCT secondary analyses will be performed based on actual treatment received, appropriate randomization performed, and appropriate randomization performed with optimal intervention shock timing (shock 4). We will also perform an a priori subgroup analysis comparing rates of survival to hospital discharge for those randomized to DSED who receive DSED after three failed successive standard shocks (early DSED or first DSED shock is shock 4-6) to those who receive DSED after six failed successive standard shocks (late DSED or first DSED shock is shock 7 or later). Last, we will perform a sensitivity analysis to examine the impact of trial phase (pilot study, pre-COVID, and during COVID) on our outcomes. The binary primary outcome, survival to hospital discharge, will be compared across the arms of DSED and VC defibrillation as an adjusted odds ratio with 95% confidence intervals (CIs) using the standard arm as the reference group.²⁷ We will use a generalized linear mixed model (GLMM; logit link) with random effects for cluster-period effect, and using fixed-effects for cluster and for the period, to account for the effect of period on the outcome, as has been recommended for the analysis of cluster crossover trials.^{28,29} The primary analysis will also adjust for the following baseline variables known to impact outcomes after out-of-hospital cardiac arrest: age, sex,

bystander witnessed arrest, bystander CPR provided, time to first arrival, public versus private location, epinephrine and antiarrhythmic use.³⁰ We will also test for effect modification by trial phase, comparing effectiveness in the internal pilot trial and the larger definitive trial. Odds ratios with 95% CIs for secondary outcomes will be calculated in a similar manner, where appropriate.

Consent Waiver

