General Characteristics: Study ID, Emergency health service, Fire service if applicable, age, sex, weight (approximate), arrest location (public/private), response time, bystander CPR, bystander AED, bystander shock, bystander witnessed, highest service level on scene (ALS vs BLS).

General Date/Time Information: Date of Call, call arrival to 911, arrival at scene (wheels stop 1st vehicle), arrival at patient side, time of first rhythm, second, etc. (all shocks), first shock, second shock, etc.(all shocks), depart scene, arrival at hospital.

Prehospital Treatment Data: Arrest occurred after EMS arrival (witnessed EMS), AED/Defib applied, total shocks delivered, number of each shocks (standard, vector change, DSED), time of first ROSC post arrest (ROSC will be defined as the restoration of a spontaneous rhythm noted on the defibrillator files with a corresponding palpable pulse noted on the paramedic ambulance call report) and termination of VF (defined as the absence of a shockable rhythm 2 minutes after each interventional or standard shock).

CPR quality characteristics: Median CCF during resuscitation, median compression rate during resuscitation, median compression depth during resuscitation.

Specific shock variables (for each shock): Pre-shock pause, post-shock pause, number of interventional or standard shocks that resulted in ROSC, rate of re-arrest post-ROSC.

Variables to be abstracted from a combination of electronic defibrillator files and the ACR

The data abstractor will use a combination of both electronic defibrillator files and the ACR to determine VF termination, time of first ROSC, as well as the number of defibrillatory shocks provided to first ROSC. All defibrillator files will be reviewed by two independent investigators blinded to the intervention to confirm VF termination as well as the subset of cases that meet the criteria for our subgroup analysis. Adjudication by a third investigator blinded to the intervention will occur should consensus be required.

Data linkage to administrative data bases at Cancer Care Ontario CCO:

The primary outcome of survival to hospital discharge will be obtained through linkage of our data with the administrative databases at Cancer Care Ontario (CCO). In addition we plan on collecting data regarding whether or not a patient had coronary angiography and/or

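### The primary survival model adjusts for epinephrine and antiarrhythmic use with no time window, so it can condition on treatment given after the randomised strategy begins

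*Combined protocol and SAP*

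**What the plan says.** Statistical Analysis and Mock Tables specifies a logistic mixed model for survival to discharge, analysed by intention to treat, and then says: "The primary analysis will also adjust for the following baseline variables known to impact outcomes after out-of-hospital cardiac arrest". The list that follows is age, sex, bystander witnessed arrest, and "bystander CPR provided, time to first arrival, public versus private location, epinephrine and antiarrhythmic use". No time limit is put on the two drug terms. For the other endpoints, "Odds ratios with 95% CIs for secondary outcomes will be calculated in a similar manner, where appropriate".

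Study Protocol fixes when the strategies diverge. The first three shocks are the same in every arm; after them, "all subsequent defibrillations will be randomized to one of the following treatment strategies". On the drugs it says only: "Epinephrine and antiarrhythmic medication (amiodarone or lidocaine) will be provided as per provincial protocol".

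The abstraction list under Data Collection includes "total shocks delivered, number of each shocks (standard, vector change, DSED), time of first ROSC post arrest" and the time of each shock. It names neither drug use nor drug times. The available text contains no analysis of survival without the drug terms. Appendices 1 and 3 were not available to this review.

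**The concern.** The six other covariates are fixed before the strategy can act. Drug use is different, because it accrues during the resuscitation that the strategy is meant to shorten. The pilot section gives reason to expect this: "ROSC was achieved in 25.0%, 39.3% and 40.0% of standard, VC and DSED groups, respectively". If ROSC comes sooner in one arm, fewer patients in that arm reach a later first dose, and having had no drug becomes partly a marker of early success. Conditioning on it compares patients within groups that the strategy itself helped to form.

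This model is the estimator for both primary comparisons, DSED versus standard and VC versus standard. Under intention to treat the target is the total effect of assignment. If part of drug use follows the assigned shocks, the adjusted odds ratio need not equal that effect, and the plan offers no other analysis that would show the difference.

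**Working it through.** **1. The text.** The strategy begins at shock 4. Nothing in the available text limits the drug terms to use before shock 4. The DSMB letter of January 2022 reports that some patients had five or more shocks before paramedics arrived, and the text does not say whether fire crews give these drugs. Universal use before shock 4 therefore cannot be assumed.

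**2. Illustration of size.** The plan has no figure of its own to reproduce here.

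Inputs from the documents: pilot ROSC R = 25.0% standard, 40.0% DSED, 39.3% VC; control survival 12%; 310 per arm.

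Assumed inputs: five shock cycles from shock 4; a share q dosed before shock 4; otherwise a 60% chance of a first dose after each failed strategy shock; none after ROSC; survival falling 10% (log scale) per extra shock; no survival without ROSC; drug odds ratio for survival 1.

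- Per-shock ROSC: p = 1 − (1 − R)^(1/5) = 0.056 standard, 0.097 DSED, 0.095 VC.
- ROSC at strategy shock k: (1 − p)^(k−1) × p.
- Survival after ROSC at shock k: s × exp(−0.1(k − 1)). Control survival of 12% gives s = 0.574. Survival is then 19.4% with DSED and 19.0% with VC.
- Undosed at ROSC on shock k: (1 − q) × 0.4^(k−1).
- DSED odds ratio without the drug term: (0.1937/0.8063)/(0.12/0.88) = 1.76. VC: 1.72.
- Wald power: Φ(ln OR/SE − 1.96). Without the term: 0.566/0.226 = 2.50, giving 71%.

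Logistic models fitted to the exact cell probabilities, with the drug term added:

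| Dosed before shock 4 | DSED OR | VC OR | SE (DSED) | Power (DSED) | OR if ROSC rises 25% to 40% but survival is 12% in both |
|---|---|---|---|---|---|
| 0% | 1.55 | 1.53 | 0.243 | 44% | 0.82 |
| 50% | 1.67 | 1.64 | 0.233 | 59% | 0.92 |
| 90% | 1.74 | 1.71 | 0.228 | 69% | 0.98 |

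In the last column the true odds ratio is 1.00, and two-sided rejection is 12%, 6% and 5%. The 0% row is an outer bound, not an expectation.

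**3. What moves the result.**

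- *Order of dose and shock.* If the first dose comes before each strategy shock, the DSED odds ratio is 1.70, 1.73 or 1.76, and the last column becomes 0.94, 0.97 or 0.99.
- *Other inputs.* The grid used 30/60/90% dosing per cycle, a 0/10/20% survival fall, and 5 or 8 cycles. The share of the log odds ratio kept is 76–90%, 90–96% and 98–99% at 0%, 50% and 90% dosed early.
- *Drug effect on survival.* With a strategy effect, a drug odds ratio of 2 keeps 80–100% of the log odds ratio, 5 keeps about 88–101%, and 15 keeps 99–107%.
- *Full null.* If the strategy changes neither ROSC nor survival, the odds ratio stays at 1.00 for drug odds ratios from 1 to 15.
- *Model closer to the plan's.* A simulation had six clusters, six periods, a cluster-period random intercept in the data, separate epinephrine and antiarrhythmic terms, and a logistic fit with cluster and period fixed effects. DSED went from 1.75 to 1.49, 1.78 to 1.64, and 1.80 to 1.73 at 0%, 50% and 90% given epinephrine before shock 4.
- *A different structure.* A model with early VF termination as the mediator and 20% versus 12% survival starts at 1.83. It gives 1.80–1.82 at 90% dosed early, 1.66–1.77 at 50% and 1.43–1.68 at 0%. Adjusting only for drug given before shock 4 leaves 1.83 unchanged.

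**The case against.** The strongest reply is that this is an ambiguity. The plan calls the terms baseline, and on a pre-strategy reading the illustration shows no bias. Appendix 1 (the provincial protocol) or Appendix 3 (the mock tables) could define a window. The abstraction list is evidently incomplete, since it omits a variable that the primary model needs; Data Collection also mentions other patient-care information, so drug times may exist. A patient shocked five times by a fire crew may get the drug after shock 3 yet before any strategy shock, so that remark in the letter does not show drug use responding to the strategy.

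The magnitudes also rest on assumed dosing patterns. At 90% dosed early the loss is slight (1.74 against 1.76; power 69% against 71%). Power at 310 per arm is not what the trial achieved: the letter reports 379 enrolled in all. With the standard errors multiplied by √(310/126), power is about 36% without the term and 34%, 29% or 21% with it. An odds ratio below 1 needs ROSC to rise with survival flat; the cohort cited in Background reported better VF termination, not ROSC, and the protocol blames late use.

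Much of this stands. Size and direction are not settled, the letter shows only that late dosing is possible, and the scenario below 1 has thin support. What does not stand is that the label resolves the matter. Calling a variable baseline sets no window, and use of a drug during resuscitation is not a baseline value unless it is limited in time.

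**Conclusion.** The concern holds and should be fixed. As written, the primary model can condition on treatment that follows the start of the randomised strategy, while the stated target is the effect of assignment. Confidence is medium, because drug timing by arm is unknown and two appendices were not seen.

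If the drugs do not affect survival and the strategy works, the consequence is attenuation and lost power, not a false positive. In the central illustration the DSED odds ratio of 1.76 falls to between 1.55 and 1.74, or to between 1.70 and 1.76 under the milder dosing order. If the strategy raises ROSC but not survival, the adjusted odds ratio can fall below 1. A strong drug benefit can reverse the direction. There is no shift if every patient is dosed before shock 4, or if the strategy changes neither ROSC nor survival. The power figures ignore clustering.

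**What to change.** Remove epinephrine and antiarrhythmic use from the primary model, and from any secondary-outcome model built the same way. Keep the other six covariates: age, sex, witnessed status, bystander CPR, time to first arrival and location. Report the model with the drug terms as a labelled sensitivity or exploratory analysis. The cost is one sentence, no new data, and the loss of two possibly prognostic covariates from the primary model.

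Restricting the terms to use before shock 4 is a weaker alternative. It needs drug times, which the abstraction list does not name. Early drug use could also still vary with an allocation that crews know from stickers on the defibrillators (Feasibility and Possible Problems) and that changes dispatch for DSED (Study Protocol). A window ending at the first strategy shock would not repair this. DSED patients receive standard shocks until a second defibrillator is secured, so that window could run longer in the DSED arm.

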Application of defibrillation pads for the second defibrillator will occur during the two-minute cycle of CPR following the third shock with minimal interruptions in CPR. All subsequent defibrillation attempts will be carried out by sequential defibrillation shocks provided by two defibrillators. To ensure shocks are not applied at the exact same moment, we will employ a short (less than one second) delay to provision of the second defibrillator shock. This will be accomplished by a single paramedic pressing the “shock button” on each defibrillator in rapid sequence as opposed to simultaneously. Dispatch deployment strategies will be employed by all paramedic services participating in the trial to ensure two defibrillators are available for all cardiac arrests in the DSED arm of the study. However, in situations when a second defibrillator is not available, the treatment will default to standard defibrillation until such time that a second defibrillator can be secured.

Randomization Strategy

Each cluster (paramedic service) will be randomized to standard defibrillation, defibrillation using VC, or DSED (see attached timeline in **Appendix 2**). All clusters will crossover between standard defibrillation, defibrillation using VC or DSED at least twice per year (at least six distinct treatment periods). Random assignment of treatment sequence will be performed by the coordinating center prior to the start of the study. Specifically, each paramedic agency will perform each arm of the study twice during the duration of the trial. Clusters will not be informed of their group assignments until necessary to make preparations to start the trial or crossover to another study strategy.

Outcome Measures

The primary outcome will be survival to hospital discharge. Secondary outcomes will include neurologic outcome at hospital discharge, ROSC, termination of VF after the first interventional shock, termination of VF inclusive of all interventional shocks, and number of defibrillation attempts to obtain ROSC.

Sample Size

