Recruitment and rates of patients presenting in refractory VF are based on local, historical data and the internal pilot RCT. Actual rates of refractory VF in the full trial may be higher or lower than projected which may impact the duration of study estimates. Enthusiasm for recruitment will be maintained with monthly updates to the paramedics and paramedic services through the activities of the EMS operations committee. The assurance of two defibrillators being available for all patients randomized to the DSED strategy has the potential to impact enrollment in this study arm but will be mitigated by changes in regional dispatch deployment in each region to assure two paramedic crews are dispatched to all cardiac arrest calls. Should one of the two intervention arms appear to be more successful than standard care, a risk of contamination of the study arm may exist for patients randomized to a perceived inferior treatment. This will be mitigated by education during the training of all paramedics on the

importance of maintaining randomization during the study, stickers applied to each service defibrillator labeled to the intervention arm as well as reminders of the importance of randomization to the validity of the study while the study is ongoing through continual education, individual and service wide paramedic feedback. Previous experience of our services in randomized controlled trials will also aid to guard against this occurrence. Defibrillation as currently proposed is Health Canada approved for both standard and VC arms of our study. We have received input from Health Canada that DSED as proposed in the study protocol is an off label use of defibrillation and its use is not within the purview of Health Canada, but does require the judgment of the local REB. We have obtained REB approval for the DOSE VF pilot from Sunnybrook Health Science Center.

Ethical and Regulatory Standards

Good Clinical Practice

The study will be conducted in accordance with both the Tri-Council Policy Statement⁴⁴ and Good Clinical Practice Guidelines.⁴⁵

Approval of the Study Protocol

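### ROSC rests partly on a pulse noted by a crew that knows the assigned strategy, yet it is outside the blinded two-reviewer check that protects VF termination

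*Combined protocol and SAP*

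**What the plan says.** ROSC is one of the secondary outcomes under Outcome Measures, and the number of defibrillation attempts to obtain ROSC is another. The definition, under Prehospital Treatment Data, has two parts: "ROSC will be defined as the restoration of a spontaneous rhythm noted on the defibrillator files with a corresponding palpable pulse", the pulse being the one entered on the paramedics' call report. In the same entry, VF termination is judged from the rhythm alone, at a fixed point two minutes after each shock.

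The section on variables taken from both the defibrillator files and the ambulance call report (ACR) assigns the work: "The data abstractor will use a combination of both electronic defibrillator files and the ACR to determine VF termination, time of first ROSC", and also the count of shocks to first ROSC. It does not say whether the abstractor is masked. It then describes the independent check, under which all defibrillator files are "reviewed by two independent investigators blinded to the intervention to confirm VF termination as well as the subset of cases that meet the criteria" for the subgroup analysis. A third blinded investigator settles disagreements. ROSC is not among the items to be confirmed.

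The protocol never calls the crews unblinded, but they cannot be otherwise. In the DSED arm, "All subsequent defibrillation attempts will be carried out by sequential defibrillation shocks provided by two defibrillators" (Study Protocol). In the VC arm the crew moves the pads. Feasibility and Possible Problems adds "stickers applied to each service defibrillator labeled to the intervention arm".

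**The concern.** Two outcomes come from the same records but do not get the same check. VF termination is a rhythm judgement at a set time, confirmed by two blinded readers. ROSC adds a judgement made by hand at the scene by someone who knows the strategy, and one abstractor assigns it. The abstractor's list of variables also includes the number of shocks of each type, so whoever completes it learns what treatment was given.

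If crews or the abstractor were readier to record or accept a pulse under one strategy, the excess would appear as a treatment effect on ROSC. It would also carry into the number of shocks to ROSC, which uses the same definition. ROSC is part of the pilot evidence offered for the trial: 25.0% with standard defibrillation, 39.3% with VC and 40.0% with DSED.

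**Working it through.** **Comparison of the two outcomes, from the protocol text**

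| | VF termination | ROSC |
|---|---|---|
| Evidence | Rhythm on the defibrillator file | Rhythm on the file and pulse on the ACR |
| Part supplied by the treating crew | None in the definition | Pulse entry |
| Assigned by | Data abstractor, masking not stated | Same |
| Two blinded reviewers | Yes | Not listed |
| Blinded adjudication | Yes | Not listed |

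The plan gives no figure that depends on how ROSC is ascertained, so there is nothing to reproduce. The following only shows how much arm-dependent recording would matter.

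**Inputs**
- True ROSC p1 = 0.25 in both arms. This is the pilot's standard-arm rate, used here as an assumption.
- f = fraction of non-ROSC patients wrongly credited with ROSC in one intervention arm only. This is an assumption with no source in the documents; the range used is 0 to 10%.
- n = 310 per arm (Sample Size), and n of about 126 per arm from the DSMB letter: (122 + 128 + 129)/3 = 126.3.
- Two-sided 5% test, normal approximation, ignoring clustering and covariates.

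**Formulas**
- Observed rate in the affected arm: p2 = p1 + (1 − p1) × f, and d = p2 − p1.
- With p̄ = (p1 + p2)/2, s0 = √[2p̄(1 − p̄)/n] and s1 = √{[p1(1 − p1) + p2(1 − p2)]/n}, the chance of a significant difference is 1 − Φ[(1.96·s0 − d)/s1] + Φ[(−1.96·s0 − d)/s1].

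**Example, f = 5%, n = 310**
- p2 = 0.25 + 0.75 × 0.05 = 0.2875, so d = 0.0375.
- s0 and s1 are both about 0.0356.
- (1.96 × 0.0356 − 0.0375)/0.0356 = 0.91. The upper tail is 0.182 and the lower tail 0.001, giving 18.3%.

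**Results**

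| f | Observed ROSC | Odds ratio | Chance of false significance, n = 310 | n = 126 |
|---|---|---|---|---|
| 0 | 25.0% | 1.00 | 5.0% | 5.0% |
| 2% | 26.5% | 1.08 | 7.1% | 5.9% |
| 5% | 28.75% | 1.21 | 18.3% | 10.3% |
| 10% | 32.5% | 1.44 | 54.1% | 25.9% |

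**Could recording alone produce the pilot difference?** To move 25.0% to 40.0% requires f = 0.15/0.75 = 20%. To reach 39.3% requires f = 0.143/0.75 = 19.1%.

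**The case against.** The strongest reply is that ROSC is not a pulse note standing alone. The file must also show a spontaneous rhythm, and the blinded reviewers already confirm on every file whether a shockable rhythm is absent two minutes after each shock. This stands as a real limit on subjective ROSC. It does not close the gap, because that reading cannot tell an organised rhythm without a pulse from one with a pulse.

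A reader might go further and object that, with no minimum duration, a pulse lasting seconds counts as success. No duration is stated. But the Background describes two minutes of CPR after each shock without a pulse check, and the Study Protocol sets rhythm analyses two minutes apart, so a very brief pulse just after a shock would seldom be sought. Whether short ROSC should count is also a choice of definition: if one strategy produced more of it, that would be a true effect on the outcome as defined. Re-arrest after ROSC is abstracted, so an imbalance could be seen.

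A reader might also take "Should one of the two intervention arms appear to be more successful than standard care, a risk of contamination of the study arm may exist" as an admission that recording will be biased. That sentence is conditional, concerns departures from the assigned treatment, and is followed by mitigations. It says nothing about recording outcomes.

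Finally, the pulse entry is in the ACR, while the blinded review covers defibrillator files. Giving reviewers the full ACR could reveal the arm. This stands, and the fix has to allow for it.

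**Conclusion.** The concern holds as a difference in protection. Two secondary outcomes, ROSC and the number of shocks to ROSC, lack the blinded confirmation that VF termination receives, although one element of ROSC is supplied by a crew that knows the strategy. That the crew knows is inferred from the interventions and the device labels, not stated in the protocol.

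The size is unknown. If 5% of non-ROSC patients were wrongly credited in one arm only, the chance of a false ROSC finding would be about 10% to 18%, depending on whether about 126 or 310 per arm are analysed. If the error fell equally on all arms, it would not of itself create a difference. The calculation ignores clustering and covariates.

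Two stronger readings are not supported. The documents do not show that arm-dependent recording occurred. Nor do they support reading the pilot's ROSC difference as an artefact, since some 19% to 20% of non-ROSC patients would have had to be misrecorded in the intervention arms alone. The primary outcome, survival to discharge, comes from linkage to administrative databases and is untouched. This is an inexpensive improvement, not a threat to the trial's main conclusion.

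**What to change.** Add ROSC to the existing blinded review, before outcomes are compared by arm.

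- The same two investigators, on the defibrillator files they already read, confirm the part of ROSC visible there: an organised, non-shockable rhythm with compressions stopped at the recorded ROSC time. Disagreements go to the same third investigator.
- Supply the ACR pulse entry and its time as a masked extract, without the rest of the call report.
- Review the pilot cases in the same way, since they enter the final analysis.
- Keep the current ROSC definition for comparability with the pilot. Alongside it, report ROSC without subsequent re-arrest as a supportive result. Re-arrest is already abstracted, but it is listed as a rate, so confirm that it is held for each patient.

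ROSC still present at hospital arrival is not proposed. The listed data give the time of first ROSC, re-arrest and arrival time, but no later ROSC time or pulse status on arrival, so a patient who re-arrested and recovered could not be classified.

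The cost is a little more reading time and preparation of the masked extract. The pulse itself still depends on the crew's note, so the review reduces the exposure without removing it.
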